1.3 Comparison of the secondary outcome measures

- Rates of clinical and bacteriologic relapse.
- Duration of diarrhoea in hours, and duration of fecal excretion of *V. cholerae* O1 or O139 in days.
- Volume of watery/liquid stool for each 6 and 24 hour of the study, and also the total amount of watery/liquid stools during the study period.
- Frequency of vomiting and the amount of vomitus, and proportion of patients with vomiting on each study day.
- Intake of oral and intravenous fluids for each 24 hour as well as the entire duration of the study.
- Proportion of patients with resolution of diarrhoea on each study day.
- Proportion of patients with a positive culture for infecting *V. cholerae* O1 or O139 on each study day.

2. Statistical methods

Data will be entered onto computer using SPSS for Windows (Version 6.0). Range check and double-entry system will be employed to facilitate data editing and cleaning. The significance of differences in continuous variables will be assessed by Student's t test for data that are normally distributed, or by Mann-Whitney U test for data which are not normally distributed. Significance of differences in the proportions will be assessed by the chi-square test, and Fisher's exact test will be employed when the expected number in any cell in the comparison is 5 or less. Survival analysis (Log Rank Test) will be done for the duration variables such as the proportions of patients with diarrhea, and a positive stool culture for *V. cholerae* O1 or O139 on each day of the study.

Ethical Assurance for Protection of Human Rights

Describe in the space provided the justifications for conducting this research in human subjects. If the study needs observations on sick individuals, provide sufficient reasons for using them. Indicate how subject's rights are protected and if there is any benefit or risk to each subject of the study.

Justifications for conducting this research in human subjects

This objective of this study is to compare clinical and bacteriologic efficacy as well as adverse events in association with therapy for children with clinically severe cholera with a single dose of azithromycin oral suspension with a 3-day course of erythromycin. Both of the study drugs are registered with the Drug Administration, Peoples' Republic of Bangladesh for use in the country.

Cholera is a human disease, and thus the efficacy of antimicrobials can only be determined in humans. Although treatment of cholera in adults is possible with a single dose of tetracycline, doxycycline and ciprofloxacin, no single-dose therapy for cholera in children has yet been possible. A single-dose therapy will not only be the most cost-effective, but will also have the advantage of being the simplest form of therapy which will eliminate the possibility of non-compliance by the patients- an important factor for emergence of resistant strains.

The objectives of the study can only be met by conducting the study in children.

Protection of human rights

The intent of the research program, the study protocol, and the informed consent form to be used in the study will be submitted to the Ethical review Committee of ICDDR,B, and the study can be initiated only after receiving a favorable response from the Committee.

Informed Consent

Since the study will be conducted in children, informed consent must be obtained from the parents or guardians of each child in accordance with the Declaration of Helsinki. It will be the responsibility of the investigator to obtain written informed consent from the them after adequate explanation of the aims, methods, anticipated benefits and potential hazards of the study. The investigator must also explain that the parents/guardians are completely free to refuse to enter their children in the study, and also to withdraw them from the study at any time. This informed consent must be obtained in the presence of a witness along with their signature, and also of signature or thumb impression (for those who can't write) of respective parents/guardians along with the date.

Use of Animals

Describe in the space provided the type and species of animal that will be used in the study. Justify with reasons the use of particular animal species in the experiment and the compliance of the animal ethical guidelines for conducting the proposed procedures.

Animals will not be involved in this study in any way

Literature Cited

Identify all cited references to published literature in the text by number in parentheses. List all cited references sequentially as they appear in the text. For unpublished references, provide complete information in the text and do not include them in the list of Literature Cited. There is no page limit for this section, however exercise judgment in assessing the "standard" length.

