DESCRIPTION OF THE RESEARCH PROJECT

Hypothesis to be tested:

Concisely list in order, in the space provided, the hypothesis to be tested and the Specific Aims of the proposed study. Provide the scientific basis of the hypothesis, critically examining the observations leading to the formulation of the hypothesis.

The hypothesis of this study is that in the treatment of cholera due to *V. cholerae* O1 or O139 in children aged 1-15 years, a single, 20 mg/kg dose (maximum of 1.0 gram) of azithromycin suspension will be as effective as the conventional, 3-day, multiple dose therapy with erythromycin suspension administered in a dose of 12.5 mg/kg (maximum individual dose of 500 mg) every 6 hours.

Specific Aims:

Describe the specific aims of the proposed study. State the specific parameters, biological functions/ rates/ processes that will be assessed by specific methods (TYPE WITHIN LIMITS).

The specific aims of the protocol are as follows:

1. Primary Aim

The primary aim of this study is to compare the clinical as well as bacteriologic efficacy of a single, 20 mg/kg dose (maximum of 1.0 gram) of azithromycin oral suspension with the conventional 3-day, 12.5 mg/kg (maximum individual dose of 500 mg) 6 hourly dose of erythromycin oral suspension in the treatment of clinically severe cholera in children due to *V. cholerae* O1 or O139.

2. Secondary Aims

The secondary aims of this study are:

- 2.1 To determine the serum and stool concentrations of both study drugs at specified times, and also to determine their serum half-lives.
- 2.2 To determine the minimum inhibitory concentration of *V. cholerae* O1 and O139 to the study drugs.
- 2.3 To monitor and compare the incidence, type and severity of adverse events in association with the study drugs.

Background of the Project including Preliminary Observations

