3.6 Determination of sample size

Sample size will be based on the proportion of clinical success of therapy in the two groups. Two previous studies conducted at ICDDR,B evaluated efficacy of erythromycin in the management of cholera in children. In one of them, the rate of occurrence of clinical success (resolution of diarrhoea) within 96 hours of initiation of therapy was 95% of the children who received 12.5 mg/kg of erythromycin suspension every 6 hours for 3 days (the dose that will also be used in this study) [39]. We expect that the rate of clinical success with a single dose of azithromycin will be similar to that of erythromycin. Thus, using the methods of Makuch and Johnson [37] for equivalence studies, we calculated the sample size as follows:

$$n = 2 \times P \times (1-P) \times (Z_{\alpha} + Z_{\beta})^2 / d^2$$

where:

P is the overall proportion of success (95%)

Z_{α} is the upper tail point of the standard normal distribution (1.645)

d (0.10) is the maximum difference in the upper 95% confidence limits

(100 x (1 - α)% for the difference in success in two treatment groups with the probability of (1 - β).

Based on the above equation we estimate a sample size of 58 patients in each treatment arm, or a total of 116 patients, with a type I error of 5% and a type II error of 20%. To account for patients whose admission stool cultures are negative for *V. cholerae* O1 or O139, or who prematurely withdraw from the study, we estimate that about 160 patients will be required to be initially enrolled in order to obtain 116 patients evaluable for analysis, however, enrollment will continue until 116 patients evaluable for analysis are obtained.

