4.1 Primary outcome measures

- Rates of clinical success
- Rates of bacteriologic success

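### The trial is posed and sized to show azithromycin within 10 points of erythromycin, but the analysis names only tests of difference, which cannot show that

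*Protocol*

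**What the plan says.** The hypothesis (Description of the Research Project, Hypothesis to be tested) is that a single dose of azithromycin "will be as effective as the conventional, 3-day, multiple dose therapy with erythromycin suspension".

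Section 3.6 follows that aim. It says "Sample size will be based on the proportion of clinical success of therapy in the two groups" and continues: "using the methods of Makuch and Johnson [37] for equivalence studies, we calculated the sample size as follows". The formula has P = 95%, Z for alpha = 1.645 and d = 0.10. It describes d as the largest difference allowed at an upper 95% confidence limit. The result is 58 per arm (116 in all), with stated errors of 5% (type I) and 20% (type II).

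Section 4.1 lists two primary outcomes, clinical success and "Rates of bacteriologic success". Data Analysis 1.2 says only that the two rates will be compared between groups. Data Analysis 2 (Statistical methods) then fixes the method: "Significance of differences in the proportions will be assessed by the chi-square test", replaced by Fisher's exact test when any expected count is 5 or less. It gives no significance level, margin, confidence interval for the difference, or equivalence or non-inferiority test. The 0.10 appears only in section 3.6.

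**The concern.** Both primary outcomes are proportions, so the chi-square/Fisher sentence is the only method the protocol gives for them. Its null hypothesis is that the two rates are equal, and a small trial can fail to reject that while the data remain compatible with a large deficit. The sample-size formula guards against accepting a drug 10 points worse. The named test does not, so the 5% and 20% error rates in section 3.6 belong to a procedure the analysis section does not contain.

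The consequence falls on the main conclusion. The Abstract Summary for the Ethical Review Committee (item 7) expects the single-dose treatment to be adopted at the hospital if it is confirmed, and section 6 points to use in large epidemics. The patients are children with severe dehydration. A conclusion of equal effectiveness should therefore rest on a criterion that controls the risk of being wrong.

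**Working it through.** **Inputs from section 3.6.** P = 0.95 in both arms, d = 0.10, Z for alpha = 1.645, type II error 20% (Z for beta = 0.8416), stated n = 58 per arm.

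**Step 1: reproduce the plan's figure.**

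n = 2 × P × (1 − P) × (1.645 + 0.8416)² / d² = 2 × 0.95 × 0.05 × 6.183 / 0.01 = 58.7 per arm.

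The stated 58 is this value rounded down (59 rounded up), a trivial difference. The same formula with 1.96 in place of 1.645 gives 74.6, so 75. A two-sided equivalence criterion (1.645 with 1.2816 for beta) gives 81.4, so 82. The stated n therefore matches a one-sided 95% confidence limit and neither of the stricter criteria.

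**Step 2: operating characteristics at 58 per arm.** I used exact binomial enumeration of all outcomes, with erythromycin success at 95%. The planned rule is Pearson chi-square, or Fisher if any expected count is 5 or less. Its two-sided 5% level is an assumption, because Data Analysis 2 gives none. The confidence-limit rule is that the one-sided 95% upper limit for erythromycin minus azithromycin lies below 0.10, computed by three interval methods.

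| True azithromycin success | Planned test non-significant | Limit < 10 points, Wald | Newcombe | Score |
|---|---|---|---|---|
| 95% | 0.989 | 0.798 | 0.734 | 0.696 |
| 90% | 0.894 | 0.308 | 0.258 | 0.225 |
| 85% (at the margin) | 0.612 | 0.069 | 0.053 | 0.045 |
| 80% | 0.305 | 0.010 | 0.007 | 0.006 |
| 75% | 0.113 | 0.001 | 0.001 | – |

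The 95% row gives the power of each confidence-limit rule, and the 85% row gives its true type I error. At 85% the planned test is non-significant with probability 0.55 if Pearson is always used and 0.69 if Fisher is always used, so the switching rule does not drive the result.

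**Step 3: size of the gap at the margin.** 0.612 / 0.05 = 12.2. Reading non-significance as equal effectiveness would carry about twelve times the stated type I error.

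**Step 4: a single data set.** Take 55/58 successes on erythromycin and 49/58 on azithromycin.

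- There are 12 failures, so 6 are expected per arm and chi-square applies. Chi-square = 2 × 3²/6 + 2 × 3²/52 = 3.35, p = 0.067.
- Difference = 0.948 − 0.845 = 0.103. SE = √(0.948 × 0.052/58 + 0.845 × 0.155/58) = 0.0557.
- One-sided 95% upper limit (Wald) = 0.103 + 1.645 × 0.0557 = 0.195.

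The planned test finds no significant difference, yet the data are compatible with a deficit of 19.5 points, almost twice the margin.

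**The case against.** The strongest reply is that the protocol nowhere says a non-significant p-value will be taken as proof of equal effectiveness. The chi-square sentence is generic and also covers baseline, relapse and daily proportions. The only criterion stated for the equivalence question is the confidence limit in section 3.6, and its mechanics might be left to a statistical analysis plan that is not shown. Part of this stands: the 61% is conditional on a reading the protocol does not state and on an assumed significance level. It does not remove the mismatch. Silence on method could be left to a later plan, but here a method is named, it covers both primary outcomes, and it does not address the trial's own hypothesis.

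A reader might infer that the planned test would pass an inferior drug most of the time. The figures support that only for a drug up to about 10 points worse (0.89 at 5 points, 0.61 at 10). At 15 points the rate is 0.31 and at 20 points 0.11.

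A reader might also infer that the sample size is wrong, or that the two primary outcomes must be tested in a fixed order with the same margin. The documents do not support either. The 58 per arm reproduces, and under the Wald limit that matches the formula the power is 79.8%. Section 3.6 ties d to clinical success only. Ordering, and any margin for bacteriologic success, are choices the protocol leaves open. The choice among Wald, Newcombe and score limits is likewise a matter of method, not an error in the plan.

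**Conclusion.** The point holds as a contradiction within the protocol. The hypothesis and section 3.6 call for a confidence limit against 0.10, while Data Analysis 1.2 and 2 provide only tests of difference. Nothing elsewhere in the protocol brings the margin or the limit into the analysis.

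The acceptance rates of 61%, 31% and 11% at 10, 15 and 20 points worse rest on three assumptions: 58 evaluable patients per arm with 95% success on erythromycin (the protocol's own planning values), a two-sided 5% test, and non-significance being read as equal effectiveness. The contradiction itself depends on none of them. It should be corrected before the data are unblinded, so that the choice between a p-value and a confidence limit is not made with the results in view.

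**What to change.** In Data Analysis 1.2 and 2, state that azithromycin will be declared as effective on clinical success if the one-sided 95% upper confidence limit (equivalently, the upper end of the two-sided 90% interval) for erythromycin minus azithromycin is below 10 percentage points. Keep chi-square and Fisher for baseline and secondary proportions.

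Name the interval method, and in section 3.6 state the power that goes with it at 58 per arm:

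- Wald: power about 80%, true type I error about 6.9%.
- Newcombe: power about 73%, true type I error about 5.3%.
- Score: power about 70%, true type I error about 4.5%.

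Section 3.6 should also say that this power applies to clinical success only. Whether to order the two primary outcomes, and whether to set a margin for bacteriologic success, is for the sponsor to decide and state.

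The cost is protocol wording; the data collected stay the same. The downside is that, unless the Wald limit is kept with its somewhat raised type I error, the stated power falls below 80% at the planned size. The sponsor would then have to accept that or enrol more patients.

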Patients eligible for study will be male (1-15 years of age) or female (5-15 years of age), who have watery diarrhea of ≤ 24 hours and signs of severe dehydration (WHO guidelines), and who have cholera vibrios identified on dark-field microscopic screening of stools. Only those patients who have ≥ 20 ml/kg body weight of stool during a 4 hour observation period following initial rehydration period will be entered into the study; only patients from whom *V. cholerae* O1 or O139 is isolated, and who stay in-hospital for three or more days will be eligible for analysis. Written informed consent will be required from the parents/guardians of all children for their inclusion in the study. Patients will be asked to remain in hospital for full five days from the initiation of drug therapy, and to return for a follow-up visit ten days after discharge. Cultures of stool will be obtained on admission to the study, and daily during hospitalization. Stool will be collected, and the volume of watery stool measured for every six hour period of the study. Major outcomes to be compared in the two treatment groups will be clinical success of therapy, defined as resolution of diarrhoea within 96 hours of initiation of study drugs, and bacteriologic success of therapy, defined as the inability to isolate the infecting strain of *Vibrio cholerae* O1 or O139 after 48 hours of therapy. Other outcomes measures examined will be the incidence of adverse reactions to drugs in the two treatment groups, the duration of watery diarrhea and positive stool cultures, and the total volume of watery/liquid stools during study.

Azithromycin is active against multiply-resistant strains of *V. cholerae* O1 or O139, it is safe for use in children, and it is widely available. If single-dose of azithromycin is found to be effective in the treatment of cholera in this study, it will be a considerable advance in treatment of cholera in children; effective single-dose therapy of childhood cholera has not been previously identified with any drug.

Principal Investigator: Last, first, middle: [name]

KEY PERSONNEL (List names of all investigators including PI and their respective specialties)

Name	Professional Discipline/ Specialty	Role in the Project
1. [name]	Internal Medicine	Principal investigator
2. [name]	Internal Medicine	Co-investigator
3. [name]	Pediatrics and Infectious Diseases	Co-investigator
4. [name]	Biochemistry	Research Officer

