2.1 Inclusion criteria

- Age / Gender: 1-15 years (male) or 5-15 years (female)
- Duration of illness: 24 hours or less
- Written informed consent for participation in the study from either parent/ guardian
- Severe dehydration according to WHO guidelines [32]
- Positive stool dark-field microscopic examination for *V. cholerae* (pre-enrollment), and isolation of *V. cholerae* O1 or O139 (post-enrollment) from a pre-therapy stool and/or rectal swab culture.

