3. OBSERVATIONS AND MEASUREMENTS

3.1 Base-line observations and management

Male children, aged 1-15 years, who are brought to the Dhaka Hospital of ICDDR, B for their watery diarrhoea of \leq 24 hours and signs of severe dehydration, and those who have not received any antimicrobial therapy for their diarrhoea will be initially screened for the study. They will be admitted into the Clinical Study Ward of the Dhaka Hospital and weighed (dehydration weight). Their vital signs and dehydration status will be recorded, and then they will be rehydrated using "Rice ORS" (3.5, 2.9, 1.5 and 50 grams of sodium chloride, trisodium citrate, potassium chloride and dried rice powder respectively for preparation of 1.0 litre of solution) or "Dhaka Solution", an intravenous polyelectrolyte solution (133,

Principal Investigator: Last, first, middle: [name]

13, 98 and 48 mmol/l of sodium, potassium, chloride and bicarbonate/1.0 litre of solution respectively) in accordance with the WHO guidelines [32]. This period will be named as "Rehydration Period" and will be about 3-4 hours in duration. During this period, a stool specimen will be sampled for dark field microscopic examination for demonstration of *V. cholerae*. Patients will be reexamined to ensure that all clinical signs of dehydration has disappeared.

3.2 4-hour, "Observation Period"

After "Rehydration Period" is over, children will be observed for another four-hour period, to be called "Observation Period". This is the maintenance phase, and the period will also be used to determine severity of illness; a stool output of \approx 5.0 ml/kg.hour during this period will be considered as indicative of a severe disease. Rice ORS will be the maintenance fluid for all patients, however, patients with severe, persistent vomiting (usually \approx 4/hour) or a very high rate of purging (usually \approx 10 ml/kg.hour) may require intravenous fluid for maintenance of hydration. Patients will be allowed to drink plain water *ad libitum* during this period, and intake and output records will be carefully maintained.

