Laboratory facilities: The clinical laboratory services of the Laboratory Sciences Division of ICDDR,B will be used for all study related laboratory investigations (tests). These laboratories are regularly used for all protocols of the Centre.

Equipments: No equipment other than those required for routine clinical examination of children will be required for this study.

Data Analysis

Describe plans for data analysis. Indicate whether data will be analyzed by the investigators themselves or by other professionals. Specify what statistical softwares packages will be used and if the study is blinded, when the code will be opened. For clinical trials, indicate if interim data analysis will be required to monitor further progress of the study. (TYPE WITHIN THE PROVIDED SPACE).

1. Comparability of study groups

1.1 Before administration of the study drug: Age, dehydrated body weight, degree of dehydration, diarrhoea duration, vomiting frequency, and stool output during the rehydration and observation periods as well as other admission characteristics will be compared between the groups.

1.2 Comparison of primary outcome measures: Rates of clinical and bacteriologic success in the two treatment groups will be compared.

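### The two duration outcomes are to be tested by an unadjusted log-rank test with no effect estimate or interval, so a non-significant result would not show how much slower cure on a single dose remains possible

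*Protocol*

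**What the plan says.** The outcomes in question are "Duration of diarrhoea in hours, and duration of fecal excretion of *V. cholerae* O1 or O139 in days" (Protocol, Data Analysis, 1.3). Section 4.2 of the research design lists both as secondary.

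The method is in Data Analysis, 2. Statistical methods: "Survival analysis (Log Rank Test) will be done for the duration variables", with diarrhoea and positive culture by study day as the examples. The same paragraph also says that "The significance of differences in continuous variables will be assessed by Student's t test for data that are normally distributed", with Mann-Whitney U otherwise. Every method in that paragraph is a significance test. None comes with an effect measure, an interval, a covariate or a stratum.

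Several pre-treatment factors are recorded for every child. Data Analysis, 1.1 lists "Age, dehydrated body weight, degree of dehydration, diarrhoea duration, vomiting frequency, and stool output during the rehydration and observation periods" and uses them to compare the groups at baseline. Of the 4-hour observation period, section 3.2 says that "the period will also be used to determine severity of illness". Allocation (section 3.5) is 1:1 in fixed blocks of 4, with no stratifying factor named.

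**The concern.** The stated hypothesis is one of similar efficacy. For the primary clinical outcome, section 3.6 builds the sample size around a confidence limit and a margin of 0.10. For the durations the plan provides only tests of difference. A p-value above 0.05 on duration of diarrhoea would leave the reader unable to tell a close match from an imprecise comparison.

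The durations deserve better because clinical failure will be rare: 5% of 58 is 2.9 children per arm. Section 4.1 has a second primary outcome, bacteriologic success, so the trial does not rest on those few failures alone. Time to cessation of watery stool is nevertheless a natural place for slower cure on a single dose to show.

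There is also a question of efficiency. If pre-treatment stool output or age predicts how long diarrhoea lasts, a model that includes it has more power than the plain log-rank test. The data are already collected, but the plan uses them only for the baseline comparison and does not say what follows if that comparison shows an imbalance.

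**Working it through.** **The plan's own figure.** Section 3.6 gives n = 2P(1−P)(Zα+Zβ)²/d² with P = 0.95, Zα = 1.645, d = 0.10 and a type II error of 20% (Zβ = 0.8416). This is 2 × 0.95 × 0.05 × (2.4866)² / 0.01 = 58.7 per arm, against 58 stated. The figure reproduces, but it concerns the clinical success proportion. No power or effect size is stated for the durations.

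**Precision on duration of diarrhoea.**
- Events: 0.95 × 116 ≈ 110 resolutions by 96 hours, if both arms do as section 3.6 expects.
- Standard error of the log hazard ratio under 1:1 allocation: 2/√110 = 0.191.
- 95% interval if the observed ratio is exactly 1.0: exp(±1.96 × 0.191) = 0.69 to 1.45. A rate of resolution about 31% lower on azithromycin would still be compatible with the data.
- Rate ratio detectable with 80% power, two-sided 5%: exp[(1.960 + 0.842) × 0.191] ≈ 1.71.

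This part needs no assumption about covariates.

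**Possible gain from adjustment.** The documents give no prognostic strength for any baseline factor, so everything here rests on assumptions: 58 per arm, log-normal duration with median 42 hours, SD set so that 95% are at or below 96 hours, durations rounded up to 6-hour periods, censoring after 120 hours, diarrhoea 25% longer in one arm, and one baseline predictor.

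| Correlation of predictor with log duration | Unadjusted power | Adjusted power | Gain (points) |
|---|---|---|---|
| 0 | about 52% | about 52% | nil |
| 0.2 | about 52% | about 55% | 3 |
| 0.3 | about 52% | 56–58% | 4–6 |
| 0.5 | about 52% | 64–68% | 12–16 |
| 0.6 | about 52% | 72–74% | 20–22 |

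Ranges show two separate sets of runs. A third, smaller set (600 runs per setting, Efron handling of ties) gave 58 v 60%, 58 v 63% and 53 v 72% at correlations 0.2, 0.3 and 0.5. The level of power shifts between sets; the direction of the gain does not.

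**A second model.** With proportional hazards, a conditional rate ratio of 1.71 and a covariate whose log-rate SD is 0, 0.3, 0.5 or 0.8, unadjusted power was 82, 73, 64 and 51%. Adjusted power was 82, 78, 79 and 79%. The gain is again nil when the covariate carries no information and rises with its strength.

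**Validity of the unadjusted test.** With no treatment effect in this second model, the unadjusted test rejected in 3.8 to 5.4% of runs. Overall type I error is therefore sound.

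**Not examined.** Excretion is measured in days from daily rectal swabs (section 3.7) and will be heavily tied. None of these simulations covers it.

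**The case against.** The strongest reply is that nothing here is an error. A log-rank test is valid under randomisation, the durations are secondary, and effect estimates and covariates for secondary outcomes are commonly left to an analysis plan, which may exist but is not shown. Validity is conceded. However, the protocol does not leave the matter open: it names the test, and the whole paragraph offers only p-values while the hypothesis is one of similarity.

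A reader might infer that power is certainly being lost. The documents do not support that. No section says that age, length of illness or pre-treatment output predicts either duration. Section 3.2 uses observation-period output to grade severity for entry, not to predict time to cure. Entry rules also narrow two of the three factors: "Duration of illness: 24 hours or less" (section 2.1), and a minimum output, since only children with at least "20 ml/kg body weight of stool during a 4 hour observation period following initial rehydration period will be entered into the study" (project summary). Zero gain belongs in the range.

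A reader might also infer that unstratified allocation makes the unadjusted comparison misleading. Chance imbalance is already allowed for in the test's overall error rate.

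Finally, the log-rank test is not the only information planned. Proportions resolved and culture-positive on each study day will be compared, and a duration in hours also falls under the t test or Mann-Whitney rule. The daily proportions help descriptively but have no stated interval. The second rule leaves two possible tests for one outcome without saying which is the main one.

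**Conclusion.** The point stands as one of reporting and efficiency on secondary outcomes. The firm part is the missing estimate. As written, a non-significant result would not show how much slower cure on one dose remains compatible with the data, and with about 110 events that uncertainty is wide (0.69 to 1.45 around an observed ratio of 1.0). This rests only on the protocol's 95% success rate and 116 evaluable children.

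The adjustment part is conditional. For duration of diarrhoea the gain runs from nil to about 20 points for correlations of 0 to 0.6, under the assumed median, spread and 25% prolongation. The documents do not fix where the trial lies, and no gain can be claimed for excretion. It would go too far to call the log-rank test wrong, or to say that the primary comparison is affected.

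**What to change.** In Data Analysis, 2. Statistical methods:

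- Name as the main analysis of duration of diarrhoea (in 6-hour periods) a Cox model with treatment, observation-period stool output per kg and age; length of illness before entry is optional. Fix the covariates and the handling of ties before the code is opened.
- Report the hazard ratio with its 95% confidence interval.
- For duration of excretion, report an effect estimate with its 95% interval from a method suited to daily, heavily tied data, such as a grouped-time proportional hazards model.
- Keep the unadjusted log-rank test as a supporting check, and state that the t test or Mann-Whitney rule is not the main analysis of these two outcomes.

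The cost is a few sentences, with no new data or patients. There is a small downside. Proportional hazards must be checked (the log-normal scenario above does not satisfy it exactly), and the adjusted hazard ratio is conditional on the covariates, so it is not the same quantity as an unadjusted one.
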